4.2.4.2. Standard Implementation Arm (arm-s) Description

Following the investigator meeting each site will have a visit with either a medical science liaison or a medical lead (depending on the country) to address investigational product questions. This might include, but is not limited to, discussing the treatment, answering medical questions, and utilization of toolkits components. On-demand visits or calls with a medical representative will be available. Injection trainings will be conducted virtually at the start of the study, with additional training options available as

needed. To capture and understand a site's successful implementation on their own doing a monthly FRAME-IS will be completed by key stakeholders and are intended to capture current successes and barriers. Of note, this condition will not have access to the country specific implementation strategies developed for arm-e.

The Arm-s will contain the following components:

- 1. Investigator meeting: All site principal investigators and key staff (e.g., nurse, pharmacist) will attend the investigator meeting that will provide information on effectiveness of CAB LA+ RPV LA, study procedures, and an overview of safety information.
- 2. Medical science liaison or CAB + RPV Medical Lead will visit each clinic per standard practice in the country. These meetings will happen quarterly or at the discretion of the clinic. At this meeting, there will be the option of using the Implementation Slide kit, however, it is not a required part of this arm and is to be decided at the discretion of the Lead.
- 3. Access to toolkit component: All sites will have access to both patient level and HCP level toolkits components. See Table 6 for list of anticipated toolkit items.
- 4. Virtual injection training: All sites will have access to a virtual injection training at the start of the study and as needed throughout the study.
- 5. Monthly FRAME assessment: each month the key stakeholder(s) for each site will identify whether they made any adaptations to the implementation strategies at their site to assist in implementation of CAB LA + RPV LA.

4.2.5. Key Evaluation of Implementation Strategies & Insights

FRAME:

A measurement of implementation strategies in this study will be critical to fully understanding how sites capitalize on facilitators and overcome barriers to CAB LA + RPV LA implementation and make changes to prescribed strategies to best meet local needs. These modifications are rarely systematically captured, ultimately limiting the generalizability of results to new clinical settings. The framework for reporting adaptations and modifications to evidence-based interventions (FRAME; Stirman, 2019) allows the capture of important modifications and adaptations to interventions or implementation strategies occurring at each local site. The FRAME-Implementation Strategy (FRAME-IS) is intended to be used to track changes made specifically to implementation strategies. The FRAME-IS is a measure that can be completed monthly to provide a precise understanding of modifications, the process of modifying or adapting, and the relationship between different forms of modification and subsequent health and implementation outcomes. Given sites are encouraged to figure out how to make CAB LA + RPV LA work for their given clinic, regardless of condition they are in, capturing the nuance for each site will be important for understanding optimal implementation across Europe moving forward. Data from the FRAME-IS can inform a foundation for future optimal implementation in sites with similar characteristics. The FRAME-IS will be used with providers in both arms.

Continuous Quality Improvement (CQI):

CQI is a dynamic implementation strategy that is intended to improve evidence-based practice delivery and quality and will involve study staff participants (Colton, 2000). It is an iterative process of monitoring performance, identifying barriers, generating possible solutions, and implementing changes. The measure and impact of change will be assessed, and modifications can be made (in real time) if a desired outcome is not being achieved. PDSA Cycle supports CQI and allows it to be individualized to the context within each clinic. The participants will be taught how to utilize the CQI process to address these problems and perform mini-experiments to understand what change is most effective to achieve their goals. This will start at the first CQI meeting during the initial SWAT meeting and will continue with hourly calls ~every month for 6 months, with the option to extend. The CQI calls will start by helping identify problems/challenges, generate plans to address the challenges, and identify how to measure the change that results from the plan, so that at each call, staff study participants can discuss progress with the CQI leader and get support if additional iterations are needed. With increased comfort, staff study participants will create PDSA cycles to test, independently of the COI facilitator.

Study Toolkit:

The study toolkit is a collection of provider-facing and patient-facing materials intended to support the delivery of CAB LA + RPV LA in real-world clinical settings (Table 6). Contents include provider- and patient educational items, nurse/injector training aids, treatment scheduling and capacity planning tools, and patient-directed apps that will be made available as part of the study. In the table below, the toolkit categories are identified. Specific toolkit items will be shared at the investigator meeting. At a minimum, they will be offered at the time pointed noted in the table. However, the toolkit items are intended to be used throughout the study.

Materials	Objective	Target Audience	Timepoint Offered for Patients and Assessed by Providers
Provider/ Staff Education Materials – Web	Staff Education	Staff	Month 1monthly through End of Study
based Provider/Staff Education materials – Hard copy	Staff Education	Staff	Month 1 monthly through End of Study
Patient Education Materials – Web- based	Patient Education	Patient	Oral Lead-in, Doses 1- 3, 5

	Table 6	Study Toolkit	Components *
--	---------	---------------	--------------

Materials	Objective	Target Audience	Timepoint Offered for Patients and Assessed by Providers
Patient Education materials – Hard copy	Patient Education	Patient	Oral Lead-in, Doses 1- 3, 5
Web-based treatment planner	Scheduling	Staff	Month 1, 2, 4, 6, 8 10
Capacity Planning Tool	Sustainability	Staff	Month 4, 6, 8, 10
Implementation Slide kit	Staff Education/ Capacity Planning	Staff	SWAT meeting or MSL meetings
Patient video	Patient Education	Patient	Oral Lead-in, Dose 1
Injection Training Video	Nurse/Injector Education	Staff/Nurse or Injector	Prior to first injection, throughout the study as needed
In-person Injection Training	Nurse/Injector Education	Enhanced Arm only - Staff/Nurse or Injector	Prior to first injection, throughout the study as needed
Peer to Peer Education	Provider/ Physician Education	Physicians/staff	During enrollment, throughout study as needed
Chatbot	Appointment Adherence and FAQs	Patients (offered at some locations)	Oral Lead-in-End of Study

* Specific toolkits offered in the study will be flexible to ensure the study is offering toolkits consistent what the toolkits that are intended to be offered in routine care.

While a "toolkit" of supporting elements will be provided in this study, clinical sites will be allowed to choose how they will implement CAB LA + RPV LA delivery in their clinical setting (i.e. nurse visit during clinic hours, pre-post clinic hours, weekend hours, Tues/Thursday clinics, in hospital settings, in pharmacies, at home etc.) as well as to create and use their own clinic-developed resources. The delivery models chosen will be tracked by study staff and captured in the questionnaires and SSIs. Modifications made to the implementation process or approach during the study, e.g. who administers the injection, timing of delivery of the injection, use of support materials, etc. are permissible and encouraged in order to facilitate successful delivery of the CAB LA + RPV LA regimen. Investigators will inform the study team of their change and document the reasons why, which will be formally captured by the FRAME-IS in both conditions.

Staff Qualitative Staff Interviews and Quantitative Questionnaires:

Questionnaires and interviews will be administered to the staff study participants at three timepoints:

- Month 1 (established by site activation): Before the first patient receives the first injections at the site
- Month 5: within 4 weeks of the first patient receiving dose 3 at the site.
- Month 12: within 4 weeks of the first patient receiving their last injection (Dose 7) at the site.

Qualitative interviews will be conducted with study staff participants and to assess whether acceptability, appropriateness, fidelity, and sustainability are achievable within each site's setting. Interviews will probe for multilevel barriers to, and facilitators of, CAB LA+RPV LA implementation. Key stakeholder interviews will elicit in-depth information as these individuals have first-hand knowledge of the factors influencing local implementation. The interviews are EPIS-based (Aarons, 2011) which allows for information about characteristics of the adopters, needs and resources of each site, impact of leadership, and factors that might impact the larger system including policy changes at a local and national level.

The interviews for staff study participants will be conducted with up to approximately 4 participants of various disciplines in each clinic that play a critical role (e.g., HIV care providers, nurse/person(s) administering the injections, clinic administrator/manager(s), pharmacists).

An example of a baseline study staff participant qualitative interview can be found in Section 10.12.

The first two questionnaires will take about 15 minutes to complete. The final questionnaire will take about 25 minutes to complete. Staff study participants will be asked to answer the questions at Month 1 based on their current expectations of administering the injection, and at the following timepoints based on their current experience administering the injection. The Month 12 assessment will include the CSAT, which may be scheduled in a separate assessment period to ensure thorough completion and support for sites following the conclusion of the study.

With notification or approval by the study team, timing and format of interviews and questionnaires maybe adjusted during times of exceptional circumstances as a result of COVID-19, missed visit. etc.

Details about concepts measured in the staff study participant questionnaires can be found Section 10.11.

Patient Qualitative Interviews and Quantitative Questionnaires:

Qualitative interviews result in valid data when thematic saturation is reached in a sample being examined. Thematic saturation is estimated to occur with 6-12 interviews in the targeted study population (Hamilton, 2019). The number of interviews is set at a minimum of 6 patients interviewed and up to 75% of PSPs enrolled per site to ensure thematic saturation. This will allow for the ability to adjust the number of PSPs at a

given site to appropriately meet site specific saturation. Interviews will be administered to the PSP at two timepoints: before Dose 1 and within 4 weeks of receiving Dose 7.

Selection for Interviews- Given the goal of qualitative data is to understand a specified topic area and gain in-depth contextual understanding rather than generalizability, purposive sampling will be utilized to select patient participants for interviews. Purposive sampling will ensure that the right patient participants are included, and the targeted information/questions can be answered and thematic saturation to be obtained at each site (Hamilton, 2019).

An example of a baseline patient study participant qualitative interview can be found in Section 10.13.

Quantitative Questionnaires. The quantitative implementation data will be collected via questionnaire which will be administered to the patient study participants a Doses 1, 3, and 7 visits (questionnaires to be completed prior to receiving the injections).

Each of the patient questionnaires will take 15-20 minutes to complete. Patient study participants will be asked to answer the questions at Dose 1 based on their current expectations of receiving the CAB LA+RPV LA injections, and at the Dose 3 and 7 timepoints will ask participants to respond based on the current experience receiving the injection during the study.

Details about concepts measured in the patient study participant questionnaires can be found Section 10.10.

With notification or approval by the study team, timing and format of interviews and questionnaires maybe adjusted during times of exceptional circumstances as a result of COVID-19, missed visit. etc.

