Barriers to Implementation	Length of patient study participant visit from arrival until departure from clinic assessed at Dose 1, Dose 2, Dose 4, and Dose 5. Qualitative SSIs assessed qualitatively through Dose 7
	SSIs assessed qualitatively through Dose 7.
To evaluate Patient Study Participants experience of delivering CAB LA + RPV LA, including Acceptability Appropriateness Feasibility	QuantitativeChange in Acceptability of Intervention Measure(AIM) Score, Intervention AppropriatenessMeasure (IAM) Score, and Feasibility ofIntervention Measure (FIM) Score over time.Assessed via questionnaires at Dose 7. bQualitativeSSIs assessed qualitatively through Dose 7.
To evaluate sustainability of CAB LA + RPV LA with Study Staff Participants each clinic	Total score of the Clinical Sustainability Assessment Tool (CSAT) at Month 12.
To assess fidelity to CAB LA +RPV LA injection dosing windows	Percentage of injections occurring within target window from the target date.
Evaluate efficacy and safety measures of CAB LA + RPV LA	Proportion of participants with plasma HIV-1 RNA <50 c/mL over time
	Proportion of participants with confirmed virologic failure (CVF) over time
	Incidence of treatment-emergent genotypic and phenotypic resistance to CAB and RPV in patient study participants with CVF
	Incidence and severity of AEs, SAEs and proportion of participants who discontinue treatment due to AEs over time
To assess preference between CAB LA + RPV LA and oral ART medication received prior to entering the study	Preference between CAB + RPV LA and daily oral ART medication (received prior to entering the study) quantitatively assessed via preference questionnaire at Dose 7

a) Month 1 is established by site activation, Month 5 is ~ the 1st patient receiving Dose 3 at the site, Month 12 is ~ the 1st patient receiving Dose 7 (last dose) at the site.

b) Dose 1 is the first injection and Dose 7 is the last injection

Overall Design:

This is a single-arm, open-label interventional study in respect to the drug regimen whereby all patients enrolled will receive the same intervention of the CAB LA + RPV LA regimen with a month oral lead in at Day 1 followed by CAB LA + RPV LA injections at Month 1, Month 2 and every 2 months (Q2M) thereafter. For the implementation science aspect, this is a two-arm study where clinics will be randomized to either Enhanced or Standard Implementation Arms at the country level.

For Clinics:

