7. DISCONTINUATION OF STUDY INTERVENTION AND PARTICIPANT DISCONTINUATION/WITHDRAWAL

A participant may withdraw consent and discontinue participation in this study at any time at his/her own request. The investigator may also, at his or her discretion, discontinue the participant from participating in this study at any time (e.g., safety, behavioral or administrative reasons). If a participant withdraws from the study, he/she may request destruction of any samples taken, and the Investigator must document this in the site study records. Withdrawn participants will not be replaced.

Participants may stop study treatment permanently at any time during the study. The primary reason study treatment is permanently stopped will be collected in the eCRF.

If commercial product is not available when participants complete the Dose 7 visit, they should continue in the CAB LA + RPV LA Extension phase of the study. Should a participant permanently stop study treatment at any time during the study and prior to

commercial product being locally available, they should be advised that it is strongly recommended they enter the Long-Term Follow-Up phase of the study, in the interest of continued safety monitoring. Participants who enter the Extension Phase but permanently discontinue participation when the CAB LA + RPV LA marketed product is locally available must enter the Long Term Follow-Up Phase if they withdraw from the study due to safety-related reasons only.

Any participant not participating in the Long-Term Follow-Up phase after CAB LA + RPV LA study treatment is stopped permanently, will attend a withdrawal visit and be withdrawn from the study. Participants are not obligated to state the reason for withdrawal. However, the reasons for withdrawal, or failure to provide a reason, must be documented by the Investigator on the Completion/Withdrawal section of the electronic case report form (eCRF). Every effort should be made by the Investigator to follow-up participants who withdraw from the study.

Participants may have a temporary interruption to their study intervention for management of toxicities.

Participants may be prematurely discontinued from the study intervention for any of the following reasons:

- Adverse event / Serious adverse event
- Protocol deviation
- Intolerability of injections
- Participant lost to follow-up
- Participant or Investigator non-compliance;
- Termination of the study by the Sponsor

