Total score of the Clinical Sustainability Assessment Tool (CSAT) at Month 12	Total score of the Clinical Sustainability Assessment Tool (CSAT) will be summarized using descriptive statistics including 95% confidence intervals. Data will be summarized by month of study as actual values and change from baseline.
Percentage of injections occurring within target window from the target date.	Percentage of injections occurring within target window from the target date, will be summarized at Month 12, including 95% confidence intervals
	The patient's 'target date' is determined by their first injection date
Proportion of participants with plasma HIV-1 RNA <50 c/mL over time	The proportion of participants with HIV-1 RNA <50 c/mL, based on the snapshot algorithm, will be summarized at Dose 7, with 95% confidence intervals
	The proportion of participants with HIV-1 RNA >= 50c/mL, respectively, based on the snapshot algorithm, will be summarized at Dose 7, with 95% confidence intervals.
Proportion of participants with confirmed virologic failure (CVF) over time	Summary of proportion of participants with confirmed virologic failure (CVF) over time using the FDA Snapshot algorithm in the ITT-E population
Incidence of treatment-emergent genotypic and phenotypic resistance to CAB and RPV in patient study participants with CVF	Incidence of treatment-emergent genotypic and phenotypic resistance to CAB and RPV in patient study participants with CVF will be summarized at Dose 7, with 95% confidence intervals
Incidence and severity of AEs and SAEs over time and the proportion of participants who discontinue treatment due to AEs over time	Incidence and severity of AEs and SAEs over time, will be summarized, with 95% confidence intervals. Proportion of participants who discontinue treatment due to AEs over time will be summarized.

Endpoints	Statistical Analysis Methods
Preference between CAB + RPV LA and daily oral ART medication (received prior to entering the study) quantitatively assessed via preference questionnaire at Dose 7	The proportion of participants preferences between CAB + RPV LA and daily oral ART medication (received prior to entering the study) with be summarized at Dose 7.
Reported injection site reactions over time	Reported injection site reactions over time will be summarized
Absolute values and changes in laboratory parameters over time	Absolute values and changes in laboratory parameters over time will be summarized, with 95% confidence intervals

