	PHYSICIAN DECISION	xx (xx.x%)	xx (xx.x%)	xx (xx.x%)
	WITHDRAWAL BY SUBJECT	xx (xx.x%)	xx (xx.x%)	xx (xx.x%)
	COVID-19 RELATED	x (xx.x%)	x (xx.x%)	x (xx.x%)
	FREQUENCY OF INJECTIONS	x (xx.x%)	x (xx.x%)	x (xx.x%)
Long-term Follow-up Phase	LOST TO FOLLOW-UP			xx (xx.x%)
	WITHDRAWAL BY SUBJECT			xx (xx.x%)
	SUBJECT RELOCATED			x (xx.x%)

CONFIDENTIAL

213199

BURDEN OF PROCEDURES

x (xx.x%)

[1] Subjects may have only one primary reason.

[2] Percentages for subreasons may sum to more or less than 100%. Subjects may have more than one subreason underneath a single primary reason. Subjects are not required to indicate subreasons.

Intervention/Extension phase: status and reason for withdrawal based on date and reason collected in the study treatment discontinuation form. Long term Follow-up: completion/withdrawal based on data collected in the Study Conclusion form.

Protocol: 213199
 Population: Safety

Page 1 of 1

Table EFF_T1
 Summary of Study Outcomes (50 c/mL cutoff) at Month 12 (Intervention Phase)
 - Snapshot Analysis

Outcome	Q4W IM (N=xx)
HIV-1 RNA<50 c/mL	xx (xx%)
HIV-1 RNA>=50 c/mL	xx (xx%)
Data in window not below threshold	xx (xx%)
Discontinued for lack of efficacy	xx (xx%)
Discontinued for other reason while not below threshold	xx (xx%)
Change in ART [1]	xx (xx%)
No Virologic Data	xx (xx%)
Discontinued study due to AE or Death	xx (xx%)
Discontinued study for Other Reasons	xx (xx%)
On study but missing data in window	xx (xx%)

[1] Excludes CAB + RPV Oral Bridging and COVID-19 related temporary oral bridging with SOC.

Protocol: mid213199
 Population: Safety

Page 1 of 1

Table EFF_T2
 Summary of Study Outcomes (50 c/mL cutoff) at Month 12 (Intervention Phase)
 - Snapshot Analysis

Outcome	Q4W IM (N=xx)
HIV-1 RNA<50 c/mL	xx (xx%)
HIV-1 RNA≥50 c/mL	xx (xx%)
Data in window not below threshold	xx (xx%)
Non-COVID-19 related	xx (xx%)
Discontinued for lack of efficacy	xx (xx%)
Discontinued for other reason while not below threshold	xx (xx%)
COVID-19 related	xx (xx%)
Discontinued for lack of efficacy	xx (xx%)
Discontinued for other reason while not below threshold	xx (xx%)
Change in ART [1]	xx (xx%)
No Virologic Data	xx (xx%)
Non-COVID-19 related	xx (xx%)
Discontinued study due to AE or Death	xx (xx%)
Discontinued study for Other Reasons	xx (xx%)
On study but missing data in window	xx (xx%)
COVID-19 related	xx (xx%)
Discontinued study due to AE or Death	xx (xx%)
Discontinued study for Other Reasons	xx (xx%)
On study but missing data in window	xx (xx%)

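### Preference, end-of-treatment acceptability and the final patient interview are collected only at Dose 7, with nothing scheduled for patients who stop earlier, so the results describe completers and may overstate preference and acceptability

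*Protocol*

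**What the plan says.** Protocol Section 4.2.5 sets the interview times: "Interviews will be administered to the PSP at two timepoints: before Dose 1 and within 4 weeks of receiving Dose 7". The questionnaires are "administered to the patient study participants a Doses 1, 3, and 7 visits", completed before that visit's injection. At the first of these, patients "answer the questions at Dose 1 based on their current expectations of receiving the CAB LA+RPV LA injections"; at Doses 3 and 7 they answer from experience. The preference endpoint in the Synopsis is "quantitatively assessed via preference questionnaire at Dose 7". Section 9.4.2 plans to summarise "The proportion of participants preferences between CAB + RPV LA and daily oral ART medication" at Dose 7, and states no denominator and no rule for patients who stop before then.

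Table 1 of the protocol (Schedule of Activities) agrees with the text. The questionnaire, interview and preference rows have no mark under Withdrawal, Safety Follow-up or LTFU. The SAP's copy of the schedule has no Safety Follow-up column, and marks none of the three under Withdrawal or LTFU.

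Among the reasons for premature discontinuation, protocol Section 7 lists "Intolerability of injections". The SAP's mock table of withdrawal reasons (DISP_T2, Appendix 13) includes the subreason "FREQUENCY OF INJECTIONS". Section 7 also says that withdrawn patients are not replaced.

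**The concern.** The patient secondary objectives are barriers and facilitators, acceptability, appropriateness and feasibility, and preference over the earlier oral regimen. A patient who stops because injections are hard to tolerate or visits are too frequent has direct evidence on each. That patient is never asked for a preference and has no exit interview. If stopping is related to the answer, a summary of those who reach Dose 7 leans towards injections.

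Two uses of the data raise the stakes. Section 4.2.2 treats acceptability, appropriateness and feasibility as surrogates for adoption outside the trial. Section 9.4.2 compares patient AIM/IAM/FIM means between arms with p-values, so unequal stopping by arm could enter that comparison. The virologic endpoint is handled differently: SAP Section 7.1.3 counts patients with no evaluable viral load in the window as non-responders. No comparable rule is stated for preference.

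**Working it through.** **Coverage** (protocol Section 4.2.5 and Table 1):

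| Instrument | Before first injection | Dose 3 | Dose 7 | Withdrawal, Safety Follow-up, LTFU |
|---|---|---|---|---|
| Questionnaire with AIM/IAM/FIM | yes (expectations) | yes | yes | none |
| Interview (selected patients) | yes | no | within 4 weeks after | none |
| Preference question | no | no | yes | none |

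A patient who stops before Dose 3 gives no experience-based answer on these instruments. One who stops between Doses 3 and 7 gives a single set of scores, taken before the third injection and so based on two earlier injection visits. Neither gives a preference or a final interview.

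**The plan's own figures** (Section 9.2):
- Enrolled: 450/(1 − 0.05) = 473.7, rounded up to 474, as stated.
- Screened: 474/(1 − 0.10) = 526.7, rounded up to 527, as stated.
- Half-width for a patient mean paired difference, n = 225, SD = 1: t(0.975, 224) × 1/√225 = 0.131, as stated.
- Non-evaluable: 474 − 450 = 24, and 24/474 = 5.1%.

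**Bound on preference.** Let c completers prefer injections at rate p, and m stoppers at rate q. Over all patients the rate is (p·c + q·m)/(c + m). The documents give neither p nor q, and no discontinuation rate. The values p = 90% and q = 0 or 50%, and losses of 10% and 15%, are assumptions. Only the 5% is the plan's.

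| Loss | m of 474 | q = 0 | q = 50% |
|---|---|---|---|
| 5% | 24 | (0.90 × 450 + 0)/474 = 85.4% | (405 + 12)/474 = 88.0% |
| 10% | 47 | (0.90 × 427 + 0)/474 = 81.1% | (384.3 + 23.5)/474 = 86.0% |
| 15% | 71 | (0.90 × 403 + 0)/474 = 76.5% | (362.7 + 35.5)/474 = 84.0% |

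If all 24 preferred injections, the 5% figure would be (405 + 24)/474 = 90.5%. With p = 80% and 5% loss, the values are 75.9% (q = 0) and 78.5% (q = 50%).

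**Scale against sampling error.** For p = 90% and n = 450, the 95% half-width is 1.96 × √(0.9 × 0.1/450) = 2.8 points. The shift at 5% loss is 4.6 points if q = 0 and 2.0 points if q = 50%, so only the extreme case exceeds it.

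**Mean scores.** The shift is the share missing times the gap. At 5% loss and an assumed 1-point gap on the 5-point scale, 24/474 × 1 = 0.05, below the 0.131 half-width. At 10% and 15% loss it is 0.10 and 0.15.

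**The case against.** The case on the other side has real weight.

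- *Patients who stop are not wholly absent.* The Dose 1 questionnaire and first interview precede any injection, and patients who stop after Dose 3 have answered once from experience. The SAP schedule also has a treatment satisfaction questionnaire at Day 1 and Doses 1, 3 and 7. A reader might infer that all patient-reported data come only from patients still on injections; the schedule does not support that. What stands is narrower: preference, end-of-treatment scores and the final interview.
- *Reasons for stopping are recorded.* The primary reason goes into the eCRF, the SAP tabulates subreasons, and its discontinuation listing shows implementation arm. This helps with barriers, but a coded reason is not a preference answer, an acceptability score or an interview.
- *The survey analysis plan is separate.* SAP Section 3 defers survey and interview reporting to a document not available here, which may set a denominator and a missing-data rule. It could not supply answers that were never collected.
- *Timing is flexible.* Section 4.2.5 lets timing and format change for COVID-19, missed visits and similar circumstances. Discontinuation is not named.
- *Interviews are purposive.* They are meant for depth, so an argument about biased proportions does not apply to them. Their loss is one of content: accounts of failed delivery.
- *The plan calls preference a Dose 7 summary.* It nowhere claims that Dose 7 responders stand for everyone treated.

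**Conclusion.** The gap is in data collection and is certain from the schedule. Its effect on the estimates is plausible but not shown. A reader might infer that preference and acceptability are overstated as a matter of fact. The documents do not support that: they give no preference rate, patient score or discontinuation rate, and the direction is inferred from the listed reasons for stopping. They also give no stopping rate by arm, so bias in the between-arm comparison is only a possibility. A wish to return to tablets is not a listed reason; Section 7 has only the general one of participant request.

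On the stated assumptions, preference at the plan's 5% loss falls from 90% to between 85.4% and 88.0% as the share of stoppers who prefer injections goes from none to half. The 4.6-point shift is a worst case. The 5% is a non-evaluable share, not a discontinuation rate. The 474 are all enrolled patients, including any who stop during the oral lead-in, and the documents do not allow a split. Mean AIM/IAM/FIM would hardly move, so the case rests on preference and the final interview. These are secondary outcomes, but answers not collected when patients stop may be unrecoverable, and collecting them costs little.

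**What to change.** 1. **Schedule of Activities and Section 4.2.5.** For any patient who stops after at least one injection and before Dose 7, give the patient questionnaire and preference question at the discontinuation contact, and hold the exit interview if the patient was selected for interview. The contact is whichever applies: last on-treatment visit, withdrawal visit, remote safety follow-up call or, failing these, first LTFU visit. Attaching the form to the withdrawal visit alone would miss patients, because footnote m to Table 1 limits that visit to those not entering LTFU who have ongoing adverse events or laboratory abnormalities. The first LTFU visit is a last resort: it falls at Month 3 after the last dose, when patients are expected to be on another regimen.

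2. **Section 9.4.2 and the separate survey analysis plan.** Keep the Dose 7 responder summary. Add preference among all patients who received at least one injection, with a sensitivity bound that counts stoppers without an answer as not preferring injections. State both denominators.

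The cost is one schedule row, a form of 15 to 20 minutes for a small number of patients, exit interviews for those selected, and one analysis paragraph. Some responses will be incomplete, and the added figure may be less favourable than the Dose 7 one. No treatment or visit rule changes.
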